Rationale: Incisional hernias (IH) are a frequent complication after abdominal surgery. Prevalence of an IH varies depending on the previous abdominal procedure but could be as high as 70% in high-risk patients after open surgery. To investigate different fascia closure techniques in the prevention of IHs, the STITCH trial (NCT01132209) was designed, a randomized controlled trial in which 560 patients were included between October 2009 and March 2012. They compared two different closure techniques for closure of a midline incision in adult patients undergoing an elective abdominal laparotomy. Patients were randomly assigned to the intervention group (small bites 5 mm x 5 mm) or the control group (large bites 1 cm x 1 cm). It showed that small bites are much more effective than large bites in the prevention of an incisional hernia when closing a midline incision.

So far, it has not been studied whether there is still a long-term difference in incidence of incisional hernia between the small bites and the large bites group.

Objective: The primary objective of this study is to determine the difference in incidence of IH between the small bites and the large bites group after 10 years of follow-up from time of randomization in the STITCH trial. The secondary objectives are to measure quality of life (QoL), body image and cosmetic results, and abdominal wall function through questionnaires and physical examination in those patients who are still alive.

Study design: Assessment of long-term follow-up (10-13 years) of a randomized controlled multicenter study based on retrospective review of patient files and relevant imaging of the entire trial population, as well as questionnaires and physical and radiological examination of patient who are still alive.

Study population: Of the 560 included patients in the original STITCH trial, 545 completed the 1-year follow-up.

Intervention (if applicable): Not applicable.

Main study parameters/endpoints: The primary outcome measure is the 10-year midline incisional hernia rate. The primary endpoint will be determined for the 545 patients of the original intention-to-treat population using Kaplan Meier analysis. In patients who died during follow-up, this will be evaluated by reviewing the available medical charts and radiological studies. CT-scans of the abdomen will be evaluated by the study-team. If CT imaging is not available, documented findings during physical examination by the relevant medical specialist will be considered. Patients being still alive with written informed consent to be contacted will be approached for their willingness to participate in this follow-up study, and after consent, we will reassess CT scans for an incisional hernia. All patients who are still alive and want to participate in this study will be asked to visit the hospital once for physical examination and an ultrasound of the abdominal wall. Secondary outcome parameters include QoL and cosmetic outcome, Patients still alive with consent for participation will be sent the following questionnaires: MOS SF-36 and EQ-5D (QoL), Dresden Body Image Questionnaire (body image), Body Image Questionnaire (cosmesis), Hernia-Related Quality of Life Survey (abdominal wall function). Furthermore, readmission and surgical intervention rates related to midline IH will be determined for the entire study population.

Nature and extent of the burden and risks associated with participation, benefit and group

relatedness: Undergoing an ultrasound, physical examination and completing several questionnaires may be considered burdensome for the patient.

1. INTRODUCTION AND RATIONALE

Incisional hernias are a frequent complication after abdominal surgery. According to Korenkov et al. the definition of an incisional hernia is: "any abdominal wall gap with or without bulge in the area of a postoperative scar perceptible or palpable by clinical examination or imaging"(1). Prevalence of an incisional hernia varies depending on the previous abdominal procedure but could be as high as 70% in high-risk patients after open surgery (2-4). In the last decade, a total of over 84,000 patients in the Netherlands were diagnosed with an incisional hernia and more than 44,000 surgeries have been performed to repair the incisional hernia (5).

An incisional hernia can become symptomatic with the need for surgical repair. Symptoms such as pain, incarceration and decreased abdominal wall function (AWF) can occur. In addition, an incisional hernia can have a major impact on body image and quality of life (QoL) (6).

To investigate different fascia closure techniques in the prevention of incisional hernias, the STITCH trial was designed. The original STITCH study (NCT01132209), a randomized controlled trial in which 560 patients were included between October 2009 and March 2012, compared the two different closure techniques for closure of a midline incision (7). Adult patients undergoing elective abdominal laparotomy were randomly assigned to the intervention group or the control group. In the intervention group, the fascia was closed with small tissue bites of 5 mm every 5 mm and in the control group with large tissue bites of 1 cm every 1 cm. Of the 560 included patients in the original STITCH trial, 545 completed the 1-year follow-up. After 1-year follow-up, 21% of patients in the "large bites" group, the control group, had developed an incisional hernia versus 13% of patients in the intervention, "small bites" group. Thus, that showed that small bites are much more effective than large bites in the prevention of an incisional hernia when closing a midline incision (7). However, the majority of incisional hernias will become apparent and symptomatic in the first five years after surgery (8).

So far, it has not been studied whether there is still a long-term difference in incidence of incisional hernia between the small bites and the large bites group. We would like to propose assessment of the long-term follow-up of the patients included in the original STITCH trial to determine if the small bites are still effective in the long-term (10 year follow-up) in preventing incisional hernia.

2. OBJECTIVES

Primary Objective:

The primary objective of the original STITCH trial was reduction of the incidence of an incisional hernia after open, elective abdominal surgery. The primary objective of the present study is to determine the difference in incidence of incisional hernia between the intervention group and the control group of the original STITCH trial after 10 years of follow-up from the time of randomization,.

Secondary Objectives:

The secondary objectives of this follow-up study are to measure quality of life (QoL), body image and cosmetic results and abdominal wall function in those patients who are still alive.

[figure not shown]
In addition, all information is collected regarding the abdominal wall hernia (presence, location, duration, size, recurrence, repair) and other abdominal wall related complications such as: open abdomen, enterocutaneous fistula, wound problems, burst abdomen, number of abdominal reoperations, number of hospital admissions (and total days) with/without development of ileus.

STUDY DESIGN

The original STITCH trial (NCT01132209) was a multicenter double-blind prospective randomized controlled trial who randomly assigned 560 patients between October 2009 and March 2012 in the intervention group (small bites) or in the control group (large bites). Ultimately, 268 patients were included in the intervention group and 277 patients in the control group. A total of 545 patients.

This current study is a long-term (10-13 years) follow-up of the original STITCH trial.

The flowchart below graphically depicts the process of approaching the patients who were included in the original STITCH trial. On the original informed consent form of the STITCH trial patients were asked if they agreed to being contacted for a follow-up study after completion the original trial.

4. STUDY POPULATION

4.1 Population (base)

All 545 patients who were included in the original STITCH trial (NCT01132209) between October 2009 and March 2012.

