4.4 Sample size calculation

The original STITCH trial ended up with 545 patients completing the 1-year follow-up.

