10. STATISTICAL ANALYSIS

10.1 Primary study parameter(s)

We will analyse the primary outcome for the 545 patients using Kaplan Meier analysis and log-rank test to compare the two trial groups based on an intention-to-treat basis (7). Statistical analyses will be performed using IBM® SPSS® Statistics Version 29. In the case of missing data, a regression model is used to estimate the missing values.

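### The primary analysis set of 545 is labelled intention-to-treat, but by the protocol's own account it is the 1-year completers among 560 randomised patients

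*Protocol*

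**What the plan says.** The protocol uses two numbers for the patients of the original trial.

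- **560 randomised.** The Study design section says the original trial "randomly assigned 560 patients between October 2009 and March 2012 in the intervention group (small bites) or in the control group (large bites"). The Summary and the Introduction also give 560 as the number included.
- **545 completers.** The Introduction states: "Of the 560 included patients in the original STITCH trial, 545 completed the 1-year follow-up". The Summary says the same, and section 4.4 repeats it: "The original STITCH trial ended up with 545 patients completing the 1-year follow-up".

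Section 4.1 then describes the base population as "All 545 patients who were included in the original STITCH trial (NCT01132209) between October 2009 and March 2012". The Study design section gives the split: "Ultimately, 268 patients were included in the intervention group and 277 patients in the control group".

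The analysis text uses the smaller number. The Summary (main study parameters) says: "The primary endpoint will be determined for the 545 patients of the original intention-to-treat population using Kaplan Meier analysis". Section 10.1 says: "We will analyse the primary outcome for the 545 patients using Kaplan Meier analysis and log-rank test to compare the two trial groups", on an intention-to-treat basis. The primary objective in section 2 counts the 10 years from randomisation.

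Other parts carry no such limit. The study design paragraph of the Summary plans review of files and imaging for the whole trial cohort. Section 11.2 approaches living patients who were in the original trial, subject only to the tick-box about future contact. Section 8.3 sets no 1-year condition on record review, and section 8.5 says every patient is already being asked.

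**The concern.** Completing 1-year follow-up is known only after randomisation. A set defined by it is not intention-to-treat, and a curve that starts at randomisation but admits only those who completed year 1 selects on later information. If patients left that set for reasons linked to the closure technique, the comparison would lose the protection of randomisation.

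The restriction is also unnecessary for the chosen method. A missed 1-year assessment can justify leaving a patient out of a 1-year proportion. Kaplan-Meier, however, accepts partial follow-up through censoring. The protocol's data sources (charts and CT of deceased patients; CT, examination and ultrasound of living ones) do not depend on the 1-year visit, so a patient who missed it may still have usable later data.

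At stake are the correctness of the primary analysis set, any later data that the 15 patients may have, and a clear instruction on whether to look for those data.

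**Working it through.** **Inputs.** 560 randomised (Study design); 545 completers (Introduction, section 4.4); arms of 268 small bites and 277 large bites (Study design); 1-year hernia rates of 13% and 21% (Introduction).

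**Step 1: reproduce the plan's figure.** 268 + 277 = 545, so the analysis set agrees with the stated arm sizes.

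**Step 2: the gap.** 560 − 545 = 15, and 15/560 = 2.7%. No section gives the arm of these 15 or the reason they are missing.

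**Step 3: compare the definitions.** The statements about who was included cannot all hold. For one recruitment window, the Introduction and Study design give 560, while section 4.1 gives 545 as all. The Introduction and section 4.4 explain 545 as completion of year 1. If that explanation is right, section 4.1 and the intention-to-treat label are wrong. If the 545 arose in some other way, the Summary, the Introduction and section 4.4 misdescribe it. The text needs correcting in either case.

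**Step 4: scale at year 1, as bounds only.** Rounded events are 0.13 × 268 ≈ 35 and 0.21 × 277 ≈ 58.

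- Observed difference: 58/277 − 35/268 = 20.9% − 13.1% = 7.9 points (uncorrected chi-square p = 0.015).
- Let *a* of the 15 belong to small bites and 15 − *a* to large bites.
- Lower bound (all added small-bites patients have a hernia, no added large-bites patient does): 58/(277 + 15 − *a*) − (35 + *a*)/(268 + *a*).
- Upper bound (the reverse): (58 + 15 − *a*)/(277 + 15 − *a*) − 35/(268 + *a*).

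| Assumed split (small/large) | Lower bound | Upper bound |
|---|---|---|
| 7/8 | 58/285 − 42/275 = 5.1 points | 66/285 − 35/275 = 10.4 points |
| 15/0 | 58/277 − 50/283 = 3.3 points (p = 0.33) | 58/277 − 35/283 = 8.6 points |
| 0/15 | 58/292 − 35/268 = 6.8 points | 73/292 − 35/268 = 11.9 points (p = 0.0003) |

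Over all splits the range is 3.3 to 11.9 points. Under the lower-bound assignment, p first exceeds 0.05 at *a* = 3 (p = 0.058).

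**Step 5: power.** For 21% v 13% at an assumed two-sided alpha of 0.05, power is 70.1% with 545 patients and 71.1% to 71.4% with 560, depending on the split. Power is not the issue.

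**The case against.** The strongest reply has four parts.

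1. **Tracing.** A reader might infer from section 4.1 that sites would never look for the 15. The documents do not support that. The study design paragraph of the Summary and sections 8.3, 8.5 and 11.2 are not limited to 545. The clear limits are in section 4.1 and in the analysis text. The protocol is therefore inconsistent about the 15, and does not plainly drop them from tracing. This part stands.

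2. **Reasons.** Some or all of the 15 may have withdrawn consent, which section 4.3 makes an exclusion. The Summary's wording also suggests that the label was carried over from the parent trial. Both are possible. But withdrawal is itself a post-randomisation loss that should be reported by arm, and an inherited label does not make 545 the number randomised.

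3. **Scale.** The bounds concern the 1-year proportion and give every added patient in one arm a hernia, against stated rates of 13% and 21%. They say nothing direct about the 10-year estimate. Patients censored early leave all later risk sets and would barely move that estimate. This stands: only those of the 15 with retrievable later data could matter, and their number is unknown.

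4. **Consent.** Analysing all 560 with withdrawers censored at withdrawal would clash with section 4.3 as written. This also stands, so section 4.3 must be part of the correction.

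**Conclusion.** The inconsistency is certain and lies in the current text. The protocol reports 560 randomised, describes 545 as the 1-year completers, and then treats the 545 both as all included patients and as the intention-to-treat set from randomisation. The size is 15 patients, 2.7% of those randomised.

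A reader might go further and conclude that the randomised comparison is biased, or that the 1-year benefit could vanish. Neither follows. Arms and reasons are not given, so bias is possible but not shown. The range of 3.3 to 11.9 points around 7.9 is an extreme bound at year 1. It rests on event counts rounded from published percentages and on assumed splits, and is no estimate of bias at year 10.

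The benefit of correction is an analysis set that matches its label, an account of the 15, and any later data that they have. The point is worth fixing because it concerns the primary analysis and the remedy is cheap. The likely numerical effect is modest.

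**What to change.** - **Section 4.1, Summary and section 10.1:** define the intention-to-treat set as all 560 randomised patients, in the arm assigned, with time from randomisation.
- **The 15:** report them by arm and reason. Trace those not barred by section 4.3 through the existing record-review and contact routes. Censor those without later data at their last assessment.
- **Section 4.3:** reconcile it with this set. State that patients who withdrew contribute data up to withdrawal where consent allows, and are otherwise reported by arm as excluded.
- **The 545:** keep them as a sensitivity set named 1-year completers, for continuity with the 1-year report.
- **If the 15 cannot be included:** drop the intention-to-treat label and say why.

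The cost is protocol wording, at most 15 extra record searches, and a main denominator that differs from the 1-year report. The sensitivity set covers the last of these.

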4.2 Inclusion criteria

In order to be eligible to participate in this study, a subject must meet the following criteria:

- Available signed informed consent form for the original STITCH trial of the patients who are still alive. Of the patients who have died, the medical records are reviewed.
- Patients must give informed consent for the current study, the long-term follow-up of the STITCH trial.

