4.3 Exclusion criteria

A potential subject who meets the following criteria will be excluded from participation in this study:

- Patients that on the original informed consent form of the STITCH trial, checked the box that they did not want to be approached for future follow-up studies.
- Patients who withdrew their informed consent during the original STITCH trial.

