8.3 Study procedure

Of patients still alive who want to participate in the follow-up study and patients who have died, the medical record and any available radiological imaging are reviewed retrospectively by members of the study team.

All patients who are still alive and want to participate in this study will be asked to visit the hospital once for physical examination and an ultrasound of the abdominal wall. Subsequently, all those patients will be asked to complete five validated questionnaires related to quality of life, cosmesis, body image and abdominal wall function. There is no set time after randomization in the original STITCH trial when the questionnaires should be completed. Indeed, this would mean that data collection would have to spread out over a few years which is not desirable.

After the physical examination and ultrasound are performed, the patient is given a brief explanation of the five questionnaires to be completed. The patient can choose whether to complete these questionnaires digitally at home or on paper at home (and return them free of charge).

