11.3 Objection by minors or incapacitated subjects

Not applicable as no minors or incapacitated subjects are included in this study.

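### Post-trial records are reviewed for patients who have died but only with new consent for the living, so decedents are over-represented in the 10-year estimate promised for all 545

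*Protocol*

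**What the plan says.** Two rules in Protocol 4.2 govern who contributes follow-up after the original trial. For the deceased: "Of the patients who have died, the medical records are reviewed". For the living: "Patients must give informed consent for the current study, the long-term follow-up of the STITCH trial". Section 8.3 confirms the split by naming whose files are opened: "Of patients still alive who want to participate in the follow-up study and patients who have died, the medical record" and any available imaging. Living patients who decline, cannot be reached or are never approached are not named.

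Section 4.3 excludes anyone who "checked the box that they did not want to be approached for future follow-up studies", and anyone who withdrew consent during the original trial. It does not say whether this is limited to the living. Section 11.2 applies the box only to approaching living patients.

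The analysis claims more than these rules deliver. The Summary describes file and imaging review for the whole trial population, and 10.1 states: "We will analyse the primary outcome for the 545 patients using Kaplan Meier analysis and log-rank test", by intention to treat. On gaps in the data, 10.1 says only: "In the case of missing data, a regression model is used to estimate the missing values".

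**The concern.** Whether a patient is observed between the end of the original trial and year 10 depends on being dead or alive when this study starts. At every earlier time that is a future event. Censoring living non-participants at about one year therefore removes people who are known to survive and leaves reviewed decedents in place. The risk set after year 1 then holds too many future decedents.

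That matters if detected hernias arise at a different rate in the two groups, and the protocol makes a difference likely. Decedents are assessed from charts and existing imaging (8.1.1), while living participants also have an examination and ultrasound (8.3). At stake is whether the reported 10-year rate is the one that following all 545 would have produced.

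**Working it through.** **The plan's own figure.** The study-design text says "268 patients were included in the intervention group and 277 patients in the control group": 268 + 277 = 545. This reproduces. No power or sample-size figure is given for the follow-up.

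**Decedent share of the risk set after year 1.** Let D be the share who die and c the participation among the living. Living non-participants are taken as censored at about year 1 (an assumption, since the text gives them no later data). Then

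share = D / (D + (1 − D)·c)

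- D = 50%, c = 60%: 0.50 / (0.50 + 0.50 × 0.60) = 0.50 / 0.80 = 63%.
- D = 50%, c = 40%: 0.50 / 0.70 = 71%.
- D = 30%, c = 60%: 0.30 / (0.30 + 0.70 × 0.60) = 0.30 / 0.72 = 42%.

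This needs only c below 100%. D and c are not in the documents.

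**Effect on the 10-year rate.** Assumptions: 17% hernia at year 1, which matches the stated arm rates since (277 × 0.21 + 268 × 0.13) / 545 = 17%; deaths spread evenly over years 1 to 11; constant detected-hernia hazards after year 1, λD in decedents and λS in survivors. The numbers at risk are proportional to

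- nD(t) = D·(1 − (t − 1)/10)·exp(−λD(t − 1))
- nS(t) = (1 − D)·c·exp(−λS(t − 1))

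The observed hernia hazard is h(t) = (λD·nD + λS·nS) / (nD + nS), and Kaplan-Meier at 10 years = 1 − 0.83·exp(−∫h dt) over years 1 to 10. For cumulative incidence, the death hazard is hd(t) = (D/10)·exp(−λD(t − 1)) / (nD + nS), and the result is 17% + ∫S·h dt with S = 0.83·exp(−∫(h + hd)).

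Results at D = 55% (KM = Kaplan-Meier, CIF = cumulative incidence with death competing; hazards per year, decedents/survivors):

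| c | Decedent share | KM, 0.01/0.03 | CIF, 0.01/0.03 | KM, 0.03/0.015 | CIF, 0.03/0.015 |
|---|---|---|---|---|---|
| 100% | 55% | 31.9% | 28.0% | 31.0% | 27.9% |
| 80% | 60% | 31.3% | 27.2% | 31.4% | 27.9% |
| 60% | 67% | 30.5% | 26.1% | 32.0% | 28.0% |
| 40% | 75% | 29.3% | 24.8% | 32.9% | 28.0% |

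Over D of 40% and 55% and c of 40% to 80%, the KM rate is about 0.5 to 2.6 points below the all-observed KM with the lower hazard in decedents. With the higher hazard in decedents it is about 0.4 to 1.9 points above. Weighting living participants by 1/c restores nS to its full-observation value, and with it the 100% row.

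**Large-bites arm alone.** Inputs: 21% at year 1 (stated), an assumed 40% at year 10 in survivors, D = 50% with deaths spread over years 1 to 10, c = 40%. With the decedent hazard at 0.25, 0.5, 1 and 2 times the survivor hazard, KM moves 35.9% to 33.2%, 37.3% to 35.6%, 40.0% to 40.0% and 44.5% to 47.3%. At equal hazards KM does not move, but cumulative incidence falls from 35.5% to 33.5% because mortality is over-weighted.

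**Between-arm difference.** With 13% and 21% at year 1, D = 50% and hazards 0.01/0.03 in both arms:

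- all observed: 35.7 − 29.2 = 6.5 points
- 60% participation in both arms: 6.6 points
- 80% in small bites, 50% in large bites: 33.9 − 28.6 = 5.3 points

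Adding an assumed 28% at year 10 for small-bites survivors to the large-bites setting above, the largest change under equal selection is about 0.6 points (11.2 to 10.6).

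**The case against.** **The benchmark.** A reader might infer that the estimate is pushed away from the true rate of the randomised population. The documents do not support that. If decedents and survivors have different hazards, death is itself informative censoring, and the all-observed Kaplan-Meier is not a population net rate. At D = 55% and hazards 0.01/0.03 the net rate is 1 − 0.83 × (0.55·e^−0.09 + 0.45·e^−0.27) = 29.8%. The all-observed KM is 31.9%, and the unweighted KM at 60% participation is 30.5%, which is nearer. This objection stands. The defensible benchmark is the same analysis with all 545 followed, and weighting a Kaplan-Meier recovers only that.

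**The comparison.** A reader might also infer that the treatment difference is biased. The primary objective is the difference between arms, and it barely moves under equal selection. The documents show no difference in death or participation by arm. This stands as a limit on the point.

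**Every decedent included.** It is tempting to say that every deceased patient is reviewed, and that two patients who ticked the no-contact box are treated oppositely. Read literally, 4.3 already excludes the deceased one. What remains is a clash of wording between 4.2/8.3 and 4.3. Similarly, 11.3 ("Not applicable as no minors or incapacitated subjects are included in this study") is a not-applicable entry, and treating it as a filter on the living alone is an inference.

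**Size and SAP.** Size and sign rest on assumed values. The standard error of a 32% rate in about 272 patients is √(0.32 × 0.68 / 272) = 2.8 points before any censoring, as large as the worst case. Requiring consent from the living is an access constraint, not an error. The study flowchart is not reproduced in the text and may show how refusers are handled, and weighting could sit in an SAP. All fair, but the selection is set by the eligibility rules, and the missing-values sentence names neither vital status nor participation.

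**Conclusion.** The point holds as a mismatch between the data-access rules (4.2, 8.3) and the population promised (Summary, 10.1). Over-representation of decedents follows by arithmetic whenever some living patients do not take part. Its effect on the Kaplan-Meier rate, relative to full follow-up of the 545, is roughly 0 to 3 points in either direction under the assumed deaths, participation and hazards, and nil at equal hazards. Cumulative incidence can shift even then. The between-arm difference is little affected unless participation or death differs by arm; in the one unequal case shown it falls from 6.5 to 5.3 points. This does not invalidate the planned analysis, but it should be addressed because it touches the primary endpoint and is cheap to address.

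**What to change.** 1. In 10.1, keep the planned Kaplan-Meier and log-rank and add a sensitivity analysis. After the end of the original trial, weight living participants by the inverse of the participation probability among living patients, estimated by arm from the baseline data in 8.1.3; give reviewed decedents weight 1. Report weighted 10-year rates and their difference with robust standard errors. Give the same analysis as cumulative incidence with death as a competing event. In the example at 55% dead and 60% participation with hazards 0.01/0.03, weighting moves that from 26.1% back to 28.0%. Report deaths and participation by arm.
2. Reconcile the Summary, 4.2, 4.3 and 8.3 so that the no-contact and withdrawal criteria apply in the same way whether the patient is alive or dead.
3. In 4.2 and 11.2, let a living patient consent to record and CT review alone, without the visit and questionnaires, to raise participation for the primary endpoint.

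Cost: protocol wording, one extra consent option, and one additional analysis on data already held, with slightly wider intervals in the weighted results. If deceased patients who ticked the box or withdrew are excluded, their later record follow-up is lost.
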